The FDA has licensed a live attenuated VZV vaccine to prevent both chickenpox and shingles. The vaccine composition is the same for both indications. The dose varies: the dose for shingles prevention is 14 times higher than the dose for chickenpox prevention. In 1995, universal vaccination with Varivax (the brand name for the pediatric dose) became universally recommended in the US. In 2005, the results of a landmark randomized controlled clinical trial in the US, done in the Veteran's administration system, showed that administration of Zostavax (the brand name for the higher adult dose) lead to a moderate reduction in the incidence of both shingles and PHN when given to older adults. Currently, the Zostavax vaccine is FDA approved for immunocompetent adults 50 or older. ACIP recommends Zostavax at age 60 and most insurance companies follow this guideline by paying for Zostavax at age 60.

It is not clear how Zostavax works. It is generally thought that long term immune memory to VZV, set into place by childhood chickenpox, gradually wanes over time, and that a delicate equilibrium between the latent virus in neurons and the immune system finally tips in favor of the virus and the individual gets clinical shingles. Zostavax, being a live vaccine, is thought to be able to stimulate or re-stimulate a specific immune response to VZV, include the components of antibodies, T-cells with the CD4 marker, and T-cells with the CD8 marker. Because Zostavax contains all 70 proteins encoded by the VZV genome, it is thought that these immune components are stimulated quite broadly and that the vaccine elicits immune responses to many VZV proteins. To date, the research on this topic is simplistic and minimal. Our lab has developed systems to use before and after vaccine blood samples to measure in quantitative detail the CD4 and CD8 T cell immune response to each individual VZV protein.

2 Study Purpose

The overall purpose of this protocol is to study the immune responses to shingles vaccination.

3 Participant Selection

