3.1 Inclusion Criteria

Men and women who meet all of the following criteria are eligible for inclusion in this study:

- 50 years of age or older
- History of chickenpox

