3.2 Exclusion Criteria

Men and women who meet any of the following criteria are not eligible for this study:

- Previous vaccination with Zostavax or with the chickenpox vaccine.
- History of ever having had shingles.
- Been in close contact with a person who had chickenpox or shingles in the past 5 years.
- VZV seronegative
- Taking systemic suppressive regular doses of drugs with anti-VZV activity such as acyclovir, famciclovir, or valacyclovir. Episodic use is allowed. For Cohort 1: medication cannot be taken 24 hours prior to or 30 days after receiving Zostavax per CDC recommendations.
- HIV seropositive.
- Hepatitis C infection or active Hepatitis B infection.
- History of a life-threatening allergic reaction (anaphylactic/anaphylactoid reaction) to gelatin, neomycin, or any other component of shingles vaccine. Neomycin allergy manifested as contact dermatitis is not an exclusion.
- Has immunosuppression as a result of an underlying illness (e.g. leukemia, lymphoma or other malignant neoplasms) or treatment with immunosuppressive or cytotoxic drugs, or use of anticancer chemotherapy or radiation therapy.
- Has long-term use of oral or parenteral steroids (>7 days), or high-dose inhaled steroids (>800 mcg/day of beclomethasone dipropionate or equivalent) within the preceding 6 months (nasal and topical steroids are allowed).
- Women of child-bearing potential only: pregnant or planning to become pregnant 3 months post vaccination (Cohort 1 only).
- Donated blood in the past 8 weeks or planning to donate blood during the study
- Weighs less than 110 lbs
- Has any condition or medical history that would, in the opinion of the site principal investigator place the subject at an unacceptable risk of injury or render the subject unable to meet the requirements of the protocol.

Additional exclusions for skin biopsy:

1. Has an acute or chronic medical condition that, in the opinion of the investigator, would render biopsies unsafe
2. History of coagulopathy or taking medication that may cause bleeding (long term aspirin, heparin, coumadin)
3. History of keloid formation or excessive scarring
4. History of frequent cellulitis or boils (>3 episodes in past 2 years) requiring antibiotic therapy.
5. Allergy to lidocaine, silver nitrate, or mupirocin.

4 Study Procedures

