4.3 Follow-up Visits

Participants will return for follow-up visits at Day 7-14, 28, and 180. Blood will be drawn for immunological assays and VZV research serology.

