8.4 Follow-up of Adverse Events

All AEs will be followed to adequate resolution or until considered stable.

All SAEs reported to the Virology Research Clinic will be relayed to the Human Subjects Division (HSD) of the University of Washington as required by HSD policy.

9 Data Analysis Plan

Positive response to VZV proteins in lymphoproliferation assays will be determined on a per-cell-line basis surpassing this threshold: at least $2.33 \times$ median absolute deviation of all negative-control antigen samples above the median response of those same samples. This calculation has a theoretical false-positive rate of 1.0%. VZV antigen wells will be scored positive only if both replicates exceed the threshold. ORFs synthesized as fragments (eg, ORF22) were scored positive once if any fragment was deemed positive.

Antibody titers, T-cell frequencies, and T-cell breadth will be compared between the different time points using the nonparametric Friedman's test for repeated measures. If significant, subsequent analysis of measures using Dunn's test identified which time points were different from prevaccine samples. Correlation analyses will be performed using the Spearman's test. Nonparametric tests will be used because the data are likely to be highly left skewed, thus did not satisfy assumptions of normality. Two-sided P values $<.05$ will be considered statistically significant. Statistical tests and graphs were generated using Prism (v7 or greater, GraphPad Software, La Jolla, California).

10 Human Subjects Protections

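### Must the one-sentence Spearman plan fix the pairs, the visit, and level versus change from Day 0?

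*Combined protocol and SAP*

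**What the plan says.** The correlation plan in Section 9 (Data Analysis Plan) is the sentence "Correlation analyses will be performed using the Spearman's test". The same section sets the threshold: "Two-sided P values $<.05$ will be considered statistically significant".

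The neighbouring text is more specific, but about a different analysis. "Antibody titers, T-cell frequencies, and T-cell breadth will be compared between the different time points" introduces Friedman's test, and Dunn's test then "identified which time points were different from prevaccine samples". Neither the list of measures nor the prevaccine reference is tied to the correlations.

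Section 2 gives the aim: "The overall purpose of this protocol is to study the immune responses to shingles vaccination". Section 3.1 requires "History of chickenpox" and Section 3.2 excludes anyone who is "VZV seronegative". Section 4.2 and Appendix A place the Day 0 blood draw before vaccination, and Section 4.3 adds the later visits: "Participants will return for follow-up visits at Day 7-14, 28, and 180".

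**The concern.** People who have had chickenpox and are seropositive bring VZV immunity to Day 0. A later level is that starting immunity plus whatever the vaccine added. If two outcomes are correlated before vaccination, their levels at Day 28 can be correlated even when the two vaccine responses are unrelated. A significant coefficient could then be read as linked responses, which is what the study's purpose would invite. Conversely, a real link between responses can be diluted when levels are used. Because the plan does not name the quantity, a reader of a later report could not check which one was intended.

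**Working it through.** The documents give no sample size, variance or expected correlation, so there is no figure of the plan's own to reproduce.

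**Inputs.** From the documents: two-sided 0.05, Day 0 before vaccination, three later visits. Assumed: n = 12, 20 or 30; one value per participant; normal data on a log-type scale; Day 0 value B with SD 1 and between-outcome correlation r0; later level = B + C, where the change C has SD k and between-outcome correlation rC.

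**Formulas.** With C independent of B, the correlation of levels is r = (r0 + k²·rC)/(1 + k²), and that of changes is rC. The matching Spearman value is ρ = (6/π)·asin(r/2). With z = atanh(ρ)/√(1.06/(n−3)), the chance of P<.05 is about Φ(z − 1.96) + Φ(−z − 1.96).

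**Check of the formula.** r0 = 0.5, rC = 0, k = 0.5, n = 20: r = 0.5/1.25 = 0.40, ρ = 0.385, z = 1.62, chance 0.37. Simulation gave 0.374.

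**Unrelated changes (rC = 0), r0 = 0.7, n = 30, levels:**

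| k | r = 0.7/(1+k²) | ρ | z | Formula | Simulation |
|---|---|---|---|---|---|
| 0.5 | 0.56 | 0.542 | 3.06 | 0.87 | 0.877 |
| 1 | 0.35 | 0.336 | 1.76 | 0.42 | 0.444 |
| 2 | 0.14 | 0.134 | 0.68 | 0.10 | about 0.10 |
| 3 | 0.07 | 0.067 | 0.34 | 0.06 | about 0.06 |

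Over r0 = 0.3 to 0.7 and n = 12 to 30, levels give P<.05 in about 7-88% of trials for k = 0.5 to 1 and about 5-11% for k = 2 to 3. Changes give about 5%.

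**Reverse case (r0 = 0, rC = 0.5 to 0.7).** The level correlation is k²·rC/(1 + k²). For rC = 0.5 this is 0.125/1.25 = 0.10 at k = 0.5 and 2/5 = 0.40 at k = 2. Levels give P<.05 in 6-44% of trials for k = 0.5 to 1, 23-88% at k = 2 and 28-95% at k = 3. Changes give 34-99%.

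**Response that falls with the Day 0 level.** Let C = −b·B + U, with U independent of B, unrelated between outcomes and of SD k. Then:

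- levels: r = (1−b)²·r0/((1−b)² + k²)
- changes: r = b²·r0/(b² + k²)

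At b = 0.5 the two expressions are identical. With r0 = 0.7 and k = 0.5, each is 0.25 × 0.7/0.50 = 0.35. At n = 30 the formula gives 0.42, and simulation gave 43.7% for levels and 43.4% for changes. At b = 0.2 changes do protect: about 5-8%, against 6-78% for levels. Above b = 0.5 the formulas make changes the more affected quantity.

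**What this shows.** The choice can decide whether P<.05, but neither the size nor the better choice can be settled from the documents. Both depend on k and b, which would be learned from the data.

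**The case for a change.** The strongest case for a change is that two or three sentences would settle the ambiguity with no extra blood draws or assays. Section 9 does not call the correlations exploratory, and it applies the 0.05 threshold to them. Verdicts from levels and changes can differ often on the same data: at n = 20, with a Day 0-to-later correlation of 0.7 within each measure, they differed in 25% of simulated trials when baselines correlated 0.6 and changes were unrelated, and in 58% when this was reversed. The three measures named for Friedman's test alone would allow 3 pairs × 4 visits = 12 level correlations and 3 × 3 = 9 change correlations. If those 21 were independent, the chance of at least one P<.05 under the null would be 1 − 0.95²¹ = 66%. They are not independent, so the true figure is lower, and the plan does not say these are the pairs.

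Part of this stands. The sentence is under-specified, and a lone significant coefficient chosen from an unlisted set is weak evidence. But a significant correlation of levels is not a false positive. It is a true statement about levels at that visit, and harm needs an author to report it as something else, which no section plans. Sections 3.1 and 3.2 support antibody at entry but give no Day 0 spread for T-cell frequency or breadth, so the high end of the range is an assumption. Listing the pairs would document a choice without supplying a better method.

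**Conclusion.** No change to the plan. This is missing detail of a kind that analysts fill sensibly. Any reported Spearman coefficient has to name its two variables and its visit, and that tells the reader whether it concerns levels or changes. Day 0 samples are drawn for the same assays, so both quantities, and the Day 0 coefficient for the same pair, can be computed whatever Section 9 says. Friedman's test, followed by Dunn's test against prevaccine samples, addresses the vaccine response over time and is untouched. No section makes a correlation primary or ties one to safety, dosing or stopping.

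The possible effect runs from negligible (about 5-11% significant level correlations at SD ratios 2 to 3) to large (up to about 88% at ratio 0.5). This rests on the assumed 12 to 30 participants, Day 0 correlations of 0.3 to 0.7, and responses that are unrelated and independent of baseline. Requiring changes from Day 0 would not reliably cure it: at a slope of −0.5 levels and changes are equally affected, at up to about 43-44% each. The remaining safeguard is one of interpretation: a correlation of post-vaccine levels should be read as an association of levels at that visit.

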10.1 IRB Approval

Prior to the initiation of the study, the principal investigator will obtain written approval to conduct the study via the University of Washington Human Subjects Review Committee.

10.2 Informed Consent

The investigator or study coordinator will explain the purpose and nature of the study, including potential benefits and risks to the participant, to each potential participant before enrollment in the study. The participant must sign an informed consent form approved by the IRB before entering the study. All original informed consent forms must be retained by the principal investigator with the participant's records. The participant will receive a copy of the signed informed consent form.

Appendix A: Table of Procedures

Study Day	Screen	Day 0	Day 7 - 14	Day 28	Day 180	Additional Visits
Obtain Informed Consent	X					
Review Inclusion/Exclusion Criteria	X	X				
Medical History	X	X				
HIV Serology	X					
HSV Serology	X					
CMV Serology	X					
VZV Serology	X					
Hepatitis C Serology	X					
Hepatitis B Surface Antigen	X					
Blood (DNA) for HLA Typing		X				
Blood Draw for Immunological Assays		X (100)	X (100)	X (100)	X (100)	X (100)
VZV Research Serology		X	X	X	X	X
Vaccination		X ¹				
Skin Biopsy		X ²		X		

¹ Blood draw will occur prior to vaccination

² Biopsy obtained prior to vaccination
